5.7 Concomitant treatments

All patients must receive 20 mg of dexamethasone or an equivalent 30 minutes before administration of trabectedin not only as anti-emetic prophylaxis, but also because it appears to provide hepatoprotective effects. Additional anti-emetics may be administered as needed.

5.7.1 Potential Impact of other medications on trabectedin and other concomitant therapies

- ◆ Results from the population pharmacokinetic analyses (n = 831 subjects) indicated that the plasma clearance of trabectedin was 19% higher in subjects who received any concomitant dexamethasone administration relative to those who did not.
- ◆ Since trabectedin is metabolized mainly by CYP3A4, the concentrations of trabectedin in plasma are likely to be increased or decreased in patients who are co-administered drugs that potently inhibit (eg, oral ketoconazole, fluconazole, ritonavir, clarithromycin, or aprepitant) or induce (eg, rifampin, phenobarbital, Saint John's Wort), respectively, the activity of this isoenzyme. The use of potent CYP inhibitors or inducers with trabectedin should be avoided, if possible. If concomitant use of a CYP3A4 inhibitor is required, patients should be closely observed for toxicities, and dose delays and reductions should occur as per the treatment guidelines described in this protocol
- ◆ Caution should be taken if medicinal products associated with hepatotoxicity are administered concomitantly with trabectedin, since the risk of hepatotoxicity may be increased.
- ◆ Concomitant use of trabectedin with phenytoin may reduce phenytoin absorption leading to an exacerbation of convulsions. Combination of trabectedin with phenytoin or live attenuated vaccines is not recommended and with yellow fever vaccine is specifically contraindicated
- ◆ Alcohol consumption must be avoided during treatment with trabectedin due to the hepatotoxicity of the medicinal product
- ◆ Preclinical data have demonstrated that trabectedin is a substrate to P-gp. Concomitant administration of inhibitors of P-gp, e.g. cyclosporine and verapamil, may alter trabectedin distribution and/or elimination. The relevance of this interaction e.g. central nervous system toxicity has not been established. Caution should be taken in such situations.
- ◆ Caution should be taken if medicinal products associated with rhabdomyolysis (e.g. statins), are administered concomitantly with trabectedin, since the risk of rhabdomyolysis may be increased.

5.7.1.1 Concomitant anti-cancer therapy

- ◆ No concomitant anti-cancer therapy including systemic therapy, radiotherapy, or surgery while on protocol treatment is allowed.
- ◆ No concomitant other investigational agent while on protocol treatment is allowed.

5.7.1.2 Permitted medications

- ◆ The use of growth factors is permitted

6 Clinical evaluation, laboratory tests and follow-up

The schedule of evaluation as described below applies to both treatment arms. A treatment cycle is defined as 3 weeks in the experimental arm and 3 or 4 weeks in the control arm, whatever is more appropriate for the selected treatment. Disease evaluation (MRI and/or CT) should follow exactly the schedule described below, irrespective of the treatment arm.

Treatment should start within an acceptable delay from randomization. A maximum delay of 21 days is accepted.

6.1 Within 4 weeks prior to randomization and within 4 weeks prior to treatment start

All evaluations performed more than 28 days prior to treatment start must be repeated.

- ◆ Informed consent
- ◆ Medical history and demographics (age, gender, medical conditions at entry)
- ◆ Clinical examination (including WHO performance status, neurological examination, blood pressure, pulse rate, body weight, height and body temperature)
- ◆ Recording of corticosteroid dose
- ◆ Assessment of all adverse events
- ◆ Cardiac monitoring: 12-lead ECG, LVEF (MUGA or echo)
- ◆ Complete blood counts will be performed, to include hemoglobin, white blood cells, neutrophils, lymphocytes, platelets.
- ◆ A serum chemistry assessment to include at least creatinine, total bilirubin, ALT, AST, alkaline phosphatase (ALP), CPK, albumin, LDH, sodium, potassium, glucose, calcium, hepatic isoenzymes 5-nucleotidase (if applicable), GGT (if applicable).
 - ◆ Alkaline phosphatase $\leq 2.5 \times$ ULN; if alkaline phosphatase $> 2.5 \times$ ULN, ALP hepatic isoenzyme and/or 5-nucleotidase and/or gamma glutamyltransferase (GGT) must be within the normal range. Creatinine clearance will be calculated by Cockcroft and Gault formula (see Appendix E)
 - ◆ For the serum chemistry parameters not collected on the Serum Chemistry form: in case of abnormal value please record it as adverse event on the Adverse Event forms (grade, relationship, seriousness).
- ◆ A serum pregnancy test is required in women of reproductive potential within 72 hours prior to randomization (and also within 72 hours prior to treatment start). The pregnancy test is to be repeated during protocol treatment every two treatment cycles.
- ◆ HRQoL: QLQ-C30 (v3) and the BN-20 questionnaire (for more information see chapter 10).

6.2 Within 2 weeks prior to randomization and within 4 weeks prior to treatment start

Baseline tumor evaluations performed more than 28 days prior to treatment start must be repeated.

- ◆ Tumor evaluation (no more than 2 weeks prior to randomization): assessed by standard methodology using cranial MRI. CT thorax/abdomen should be performed if clinically indicated. The same method should be used for repeated measurements throughout the study.

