6.3 During treatment

The following need to be performed on day 1 of each treatment cycle or within 72 hours before:

- ◆ Clinical examination (WHO PS, blood pressure, pulse rate, body weight, and body temperature).
- ◆ Assessment of all adverse events that have occurred since the previous visit and ongoing events from previous cycles should be followed.
- ◆ Complete blood counts to include hemoglobin, white blood cells, neutrophils, lymphocytes, platelets. For the experimental arm only, additional monitoring of hematological values should occur weekly during the first two cycles of therapy, and at least once between treatments in subsequent cycles
- ◆ A serum chemistry assessment to include at least creatinine, total bilirubin, ALT, AST, ALP, CPK, albumin, LDH, sodium, potassium, glucose, calcium. For the experimental arm only, additional monitoring of serum chemistry values should occur weekly during the first two cycles of therapy, and at least once between treatments in subsequent cycles
 - ◆ If ALP > 2.5 ULN, ALP hepatic isoenzyme 5-nucleotidase and/or GGT tests must be performed; ALP hepatic isoenzyme or 5-nucleotidase and/or GGT must be within the normal range.
 - ◆ Creatinine clearance will be calculated by Cockcroft and Gault formula (see Appendix E)
 - ◆ For the serum chemistry parameters not collected on the Serum Chemistry form: in case of abnormal value please record it as adverse event on the Adverse Event forms (grade, relationship, seriousness).
- ◆ Cranial MRI every 9 weeks from randomization and if clinically indicated
- ◆ Recording of corticosteroid dose every 9 weeks
- ◆ CT thorax/abdomen only if clinically indicated; if tumorous or unclear lesions detected repeat CT every 9 weeks and if clinically indicated
- ◆ HRQoL: QLQ-C30 (v3) and the BN-20 questionnaire: regardless the treatment arm, at week 3, week 6 and week 12 after treatment start (for more information see chapter 10).
- ◆ Pregnancy test (every two cycles)

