6.5 Summary table

	Within 4 weeks prior to randomization ⁷	Within 2 weeks prior to randomization	During treatment		After treatment		
			On day 1 of each cycle or within 72 hours before	Every 9 weeks	End of treatment (30 days after last treatment administration)	Until PD every 9 weeks	After PD, every 9 weeks for the first year from randomization and every 12 weeks thereafter
Informed consent	♦						
Clinical examination	♦		♦		♦	♦ ⁸	
Medical history, demographics	♦						
Recording of corticosteroid dose	♦			♦		♦	
Adverse events assessment	♦		♦		♦	♦	
ECG	♦						
LVEF	♦						
Hematology ³	♦		♦		♦		
Serum chemistry ⁴	♦		♦		♦		
Pregnancy test	♦ ¹		♦ ¹		♦ ²		
Quality of life questionnaire (QLQ-C30 and BN20)	♦		♦ ⁵				
Tumor evaluation using cranial MRI		♦ ¹⁰		♦		♦ ⁹	
CT torax/abdomen		♣		♣ ⁶		♣ ⁶	
Survival						♦	♦

♦ mandatory

♣ if clinically relevant

1. Perform only in women of childbearing potential. The pregnancy test has to be done within 72h prior to randomization and also within 72 hours prior to treatment start and repeated during protocol treatment every two treatment cycles.

2. Pregnancy test must be repeated at 30 days and 3 months after last treatment dose.

3. Hematology test includes white blood cells, neutrophils, lymphocytes, platelets, hemoglobin counts.

Note for the experimental arm only: additional monitoring of hematological values should occur weekly during the first two cycles of therapy, and at least once between treatments in subsequent cycles.

4. Serum chemistry includes at least creatinine, total bilirubin, ALT, AST, ALP, CPK, albumin, LDH,

sodium, potassium, glucose, calcium. If alkaline phosphatase > 2.5 ULN, ALP hepatic isoenzyme and/or 5-nucleotidase and/or gamma glutamyltransferase (GGT) must be performed. Note: for the experimental arm only, additional monitoring of biochemical parameters (ALP, total bilirubin, CPK, and aminotransferases [AST and ALT]) should occur weekly during the first two cycles of therapy, and at least once between treatments in subsequent cycles.

5. QLQ-C30 (v3) and BN-20: at end of week 3/end of cycle 1, end of week 6/end of cycle 2, end of week 12/end of cycle 4 after treatment start, and at month 6 after treatment start regardless of treatment arm or progression status.

6. Only in patients with known tumorous or unclear lesions on prior CT

7. All evaluations performed more than 28 days prior to treatment start must be repeated

8. Only WHO PS

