10.3.1 HRQoL schedule - timing and location

HRQoL questionnaires must be filled out at the hospital when patients come for a scheduled visit according to the EORTC “Guidelines for administration of questionnaires” (see Appendix G). The pre-treatment questionnaires must be filled within 4 weeks prior to randomization. Subsequent questionnaires are filled in as described in the time schedule in this paragraph.

Electronic copies of the HRQoL questionnaires will be sent to the institutions to be printed. Additional translations can be provided to any institution upon request via the EORTC contact person. The case report forms will include a question whether the HRQoL forms have been filled in, and if not, the reason why. The questionnaire will be handed out to the patients by the investigator or a study nurse prior to seeing the doctor for clinical evaluations. The patient should complete the questionnaires by her/himself in her/his own language **prior** to seeing the treating physician at the outpatient clinic as completely and accurately as possible. It is recommended that a key person (e.g. research nurse) at each center should be responsible for questionnaire data collection in order to optimize the compliance of the patient and to ensure the completeness of the data.

During the study, compliance with completing questionnaires will be investigated at each time point. The compliance of the HRQoL assessments will also be reviewed twice a year and will be part of the descriptive report.

The time windows for eligible HRQoL assessments will be as follows:

Assessment	Time window
Baseline	Can be completed before or on the day of start of protocol treatment but no earlier than 28 days before.
Week 3 (End of cycle 1)	To be completed during the third week after treatment start while on protocol treatment. If 3 weekly chemotherapy regimen: can be completed during the third week of the first cycle of chemotherapy (D15-D21 of cycle 1).
Week 6 (End of cycle 2)	To be completed during the sixth week after treatment start while on protocol treatment. If 3 weekly chemotherapy regimen: can be completed during the third week of the second cycle of chemotherapy (D15-D21 of cycle 2).
Week 12 (End of cycle 4)	To be completed during the twelfth week after treatment start while on protocol treatment. If 3 weekly chemotherapy regimen: can be completed during the third week of the fourth cycle of chemotherapy (D15-D21 of cycle 4).

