10.3.2 Compliance

Missing data may hamper assessment of HRQoL in clinical trials. This may be because centers do not collect the questionnaires at the appropriate time (unit non-response), and because patients may miss questions within the questionnaires (item non-response). The latter problem occurs less than 2% on average and should not be a problem. The former problem will be minimized by ensuring that participating centers are properly informed and motivated towards HRQoL assessment. During the study, compliance with completing HRQoL questionnaires will be investigated at each time point. The compliance of the HRQoL assessments will also be reviewed twice a year and will be a part of the descriptive report by Data Center for the Group's plenary sessions. The compliance rate between the 2 arms will be compared at each time point using a chi-square test. In order to adjust for the multiplicity of the tests, a Bonferroni adjustment will be made by which each test will be performed at the 0.01 significance level. Should serious volumes of missing questionnaires occur (below 65% at any assessment point) then the protocol writing committee would review the HRQoL assessment in the trial.

Available patient numbers will diminish during the trial due to progression, death, or loss to follow-up. Given the low prognosis of the patient population, the HRQoL assessments appear more frequently early on (first 3 cycles) and only one later follow-up visit is required.

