10.4 Statistical considerations

The primary HRQoL endpoint that is considered relevant for this study is **global QOL**. The following scales will be considered as secondary HRQoL endpoints: **role functioning, physical functioning, cognitive functioning, fatigue, diarrhea, and nausea and vomiting**. The other available scales will only be analyzed on an exploratory basis.

A difference of 10 points on the 100-point QLQ-C30 scale between the two arms will be considered as clinically relevant. The standard deviation of this scale is approximately 20 points. With the 1-sided alpha set at 10%, and a target difference of 10 points (effect size of 0.5), a minimum of 89 patients (in a 2:1 randomization) yields 80% power and 76 patients would yield 75% power. Therefore, this study is sufficiently powered to detect differences in HRQoL.

Data will be scored according to the algorithm described in the EORTC scoring manual. All scales and single items are scored on categorical scales and linearly converted to 0-100 scales.

Changes in HRQoL scores over time will be evaluated with summary statistics. The following two summary statistics will be used:

- ◆ During treatment: the change from baseline score to the worst score (ie minimum for functioning and global health scale; maximum for symptom scales) reported during treatment per patient will be compared.
- ◆ After treatment: the change from baseline score to the score at month 6.

Both summary statistics will be displayed via mean, median and standard deviation per treatment arm. Treatment differences will be displayed via mean differences and corresponding 90% confidence intervals. Treatment comparisons will be done via non-parametric logrank tests for the selected primary and secondary scales. Both statistical and clinical significance will be assessed.

Supportive analyses will be done by calculating the proportion of patients who experience a clinical significant deterioration (i.e. 10 point or more worsening) for both summary statistics.

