10.4.1 Missing data

Missing data is a potential major source of bias in HRQoL assessment.

In order to check the potential impact in the study, the compliance mechanism will be investigated prior to initiating the HRQoL analysis. Characteristics of patients with and without valid HRQoL data will be compared and trends over time per dropout pattern will be investigated. Model building will be used in order to investigate whether the compliance mechanism is linked to selected prognostic variables.

Once the main analysis is completed, sensitivity analyses will be undertaken to verify the robustness of the results vis-à-vis the missing data by imputation of plausible values. In case overall compliance is deemed too low (<50%), only an exploratory analysis will be performed in lieu of the main analysis.

11 Translational research

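### The on-treatment HRQoL summary (worst score per patient) depends on how many forms a patient completes, and control patients are likely to complete fewer

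*Combined protocol and SAP*

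**What the plan says.** **Schedule.** The opening of section 6 sets a 3-week cycle for trabectedin and "3 or 4 weeks in the control arm, whatever is more appropriate for the selected treatment". Section 6.3 places on-treatment assessments on day 1 of each cycle or in the 72 hours before, and lists the questionnaires there "regardless the treatment arm, at week 3, week 6 and week 12 after treatment start". Section 10.3.1 sets the windows as the third, sixth and twelfth week after treatment start, while on protocol treatment. It offers cycle-based timing for one kind of regimen only: "If 3 weekly chemotherapy regimen: can be completed during the third week of the first cycle of chemotherapy". Footnote 5 of table 6.5 equates the weeks with cycle ends, for example "end of week 12/end of cycle 4 after treatment start".

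**Place.** Section 10.3.1 says "HRQoL questionnaires must be filled out at the hospital when patients come for a scheduled visit". Appendix G rules out home or mailed completion unless the protocol states otherwise, and it does not. Section 6.3 adds weekly blood monitoring in the first two cycles for the experimental arm only.

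**Analysis.** The during-treatment summary in 10.4 is "the change from baseline score to the worst score", taken per patient and shown as a mean difference with a 90% confidence interval. Global QoL is the primary HRQoL scale. No rule covers patients with different numbers of forms.

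**Safeguards.** Section 10.3.2 compares compliance between arms at each time point at the 0.01 level and has a review clause: "Should serious volumes of missing questionnaires occur (below 65% at any assessment point". Section 10.4.1 adds "In case overall compliance is deemed too low (<50%), only an exploratory analysis will be performed", and plans imputation as a sensitivity analysis after the main one.

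**The concern.** The worst of three scores is lower, on average, than the worst of one, even when nothing has changed in the patient. If one arm systematically has fewer forms, the comparison of worst scores is biased in that arm's favour. Here the arm with fewer forms is likely to be the control arm, for two reasons: controls are expected to progress sooner, and those on a 4-week cycle have no cycle visit in two of the three windows. Trabectedin would then look worse on global QoL with no true effect. This matters because section 10 includes HRQoL in order to weigh any gain in PFS against the burden of treatment.

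**Working it through.** **1. The plan's own HRQoL figure.** Section 10.4 gives 89 patients for 80% power and 76 for 75% (2:1, one-sided 10%, difference 10, SD 20). Total = 4.5 × [20 × (z0.90 + z_power) / 10]² = 81.1 and 68.9. Dividing by the rank-test efficiency 3/π gives 85.0 and 72.1, or 87 and 75 after rounding up within arms at 2:1. These are close to the stated figures, which are not in dispute.

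**2. Calendar, counted from treatment start.** A visit may fall on day 1 of the next cycle or up to 3 days before.

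| | Week 3 | Week 6 | Week 12 |
|---|---|---|---|
| Window (days) | 15–21 | 36–42 | 78–84 |
| 3-week cycle visit | 19–22 | 40–43 | 82–85 |
| 4-week cycle visits | none (26–29) | none (54–57) | 82–85 |

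On a 4-week cycle the ends of cycles 1, 2 and 4 are weeks 4, 8 and 16, so the cycle labels do not fit. The first MRI is due 63 days after randomization, which is treatment day 64 − d for a start delay of d days: day 64 with no delay and day 43 at the maximum of 21 days. If the 72-hour allowance also applies to the MRI, it can reach day 42 only when 61 − d ≤ 42, that is, for delays of 19 to 21 days.

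**3. Time on treatment.** With the exponential PFS of section 8.1.1, S(w) = p^(w/26.09), where p = 0.15 (control) or 0.35 (trabectedin) and 6 months = 26.09 weeks. Progression-free at weeks 3, 6 and 12: control 80%, 65%, 42%; trabectedin 89%, 79%, 62%.

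**4. Effect of the number of forms on one patient.** For k equally correlated normal scores, the expected worst score lies c_k × 20 × √(1 − ρ) below the mean, with c₁ = 0, c₂ = 0.564, c₃ = 0.846. Three forms against one: 0.846 × 20 × √0.5 = 12.0 points at ρ = 0.5, and 0.846 × 20 × √0.3 = 9.3 at ρ = 0.7.

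**5. Effect on the comparison.** Simulation of 6,000 trials per setting: 57 against 29 patients, no true effect, SD 20, ρ = 0.5 or 0.7 (assumed), progression unrelated to score. Patients with no on-treatment form are excluded. Affected controls lose the week-3 and week-6 forms. The last row of each block is the share of trials with the 90% interval (Welch) wholly against trabectedin; nominal is 5%.

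| Affected controls | 0 | 7 | 14 | 29 |
|---|---|---|---|---|
| *Forms stop at progression* | | | | |
| Points, ρ 0.5 | 1.43 | 2.51 | 3.96 | 9.92 |
| Points, ρ 0.7 | 1.11 | 1.93 | 3.15 | 7.62 |
| False exclusion | 9% | 12% | 17–18% | 44% |
| *Forms stop at the next 9-week MRI* | | | | |
| Points, ρ 0.5 | 0.65 | 2.08 | 3.87 | 10.77 |
| Points, ρ 0.7 | 0.54 | 1.60 | 3.11 | 8.32 |
| False exclusion | 7% | 11–12% | 20% | 57% |

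Repeat runs of 3,000 trials gave 0.6–1.5, 1.6–2.6, 3.0–4.0 and 7.8–11.0 points, and 7–10%, 12–14%, 17–21% and 43–58%. The first column is due to earlier control progression alone. Subtracting it, the calendar adds 0.8 to 1.4 points for 7 affected controls (for example 1.93 − 1.11 = 0.82) and 2.0 to 3.2 for 14 (3.87 − 0.65 = 3.22).

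A fixed-week comparison under the same assumptions (week-by-arm means, average of the three week differences, known covariance, 2,500 trials) gave 4.2 to 6.0% for 0, 7 or 14 affected controls.

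**6. Would the safeguards act?** If compliance is otherwise full, pooled week-3 compliance with 7, 14 or 29 control forms lost is 79/86 = 92%, 72/86 = 84% and 57/86 = 66%, never below 65%. Section 10.3.2 does not say whether the 65% applies per arm; if it does, 15/29 = 52% would trigger the review. The chi-square test would notice 7 of 29 against 0 of 57 missing (p = 0.0001, or 0.0006 with continuity correction), but noticing the imbalance does not correct the comparison.

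**The case against.** **The plan already fixes the calendar weeks.** Section 6.3 requires the forms at weeks 3 and 6 in both arms, and section 10.3 makes HRQoL mandatory. A site can arrange attendance, and the calendar loss is then zero. This stands. A reader might infer that every control on a 4-week cycle will lose two forms; the documents show only that no cycle visit falls in those windows.

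**Trabectedin forms can be missed too.** Day 1 of the next cycle falls on day 22, 43 or 85, just outside each window. Delays of up to 3 weeks are allowed, and nothing says the weekly blood tests must be done at the trial hospital. This softens the contrast between arms. It remains that a 3-week visit held within the 72-hour allowance reaches every window, while a 4-week visit cannot reach weeks 3 or 6.

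**Part of the bias is not due to the calendar.** This is correct, and it is shown separately above. It supports changing the summary whatever the cycle length.

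**The increments are small against 10 points, and 10.4 assesses clinical as well as statistical significance.** Fair. An interval excluding zero together with a difference of at least 10 points occurred in 0–4% of simulated trials with no affected control, 1–7% with 7 and 3–12% with 14.

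**Compliance review, dropout-pattern checks and imputation are planned.** They detect and explore an imbalance. They leave the main comparison unchanged.

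**Remote completion for controls only would make the mode of completion differ by arm in an open-label trial.** This also stands, so the option should apply to both arms.

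**Conclusion.** The point holds as a weakness of the chosen summary, made worse by a schedule that does not fit one permitted control cycle. With no true effect, earlier control progression alone gives about 0.5 to 1.5 points against trabectedin and a false exclusion of zero in about 7 to 10% of trials. With 7 controls losing both early forms the totals are 1.6 to 2.6 points and about 11 to 14%; with 14 they are 3 to 4 points and about 17 to 21%. These figures rest on the plan's SD and PFS assumptions, an assumed correlation of 0.5 to 0.7, and progression unrelated to score.

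The share of controls on 4-week cycles is not given. A reader might take the right-hand column of the table (about 8 to 11 points, 43 to 58%) as the expected effect. It needs all 29 controls to be on 4-week cycles and all to lose both forms, so it is only an upper bound. Nor does the point reach the primary endpoint: PFS and the month-6 HRQoL summary are unaffected.

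**What to change.** 1. In 10.4, make the main on-treatment comparison one at fixed weeks, for example a mixed model with arm-by-week means at weeks 3, 6 and 12. Keep the worst score as supportive and report forms per patient by arm. Retain the imputation sensitivity analysis, because a fixed-week model removes the dependence on form counts but not bias from dropout related to unobserved scores.
2. In footnote 5 of table 6.5 and in 10.3.1, keep the calendar weeks and delete the cycle-end labels for regimens that are not 3-weekly. Allow remote completion within the window, in both arms, whenever no visit falls in it, and record the mode of completion. Appendix G permits this once the protocol says so.

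The cost is some rewording, a little more analysis of data already planned, and no extra visits. Some forms would be completed away from the hospital, without on-the-spot screening for omissions. In the control arm that is at most 2 × 29 = 58 week-3 and week-6 forms, if every control were on a 4-week cycle.
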